4.3 Exploratory endpoints

The exploratory endpoints of this study are:

1. Exploratory composite scale comparing the following among the three groups at Week 8, 12 and 26:
 - Number of events of worsening symptoms warranting the addition of antibiotics
 - Number of events of worsening symptoms warranting an increase in dose of oral

-
- corticosteroids or initiation of new oral corticosteroids
- Number of events of worsening symptoms requiring additional treatment of oral corticosteroids and/or antibiotics after completion of the initial regimen
 - Number of events of COPD exacerbation requiring re-hospitalisation
 - Number of COPD-related deaths.
2. Change in CRQ from baseline at Day 14 and Weeks 8, 12 and 26 to evaluate recovery, comparing among the three groups over time
 3. Cumulative oral/IV steroid dose from Day 1 to Day 14, and from Day 14 to Week 26
 4. Change in inflammatory blood biomarkers (IL-6, TNF- α , fibrinogen, hs-CRP, and MPO) daily during Part 1 of the study, and at Weeks 8, 12 and 26
 5. Relationship between BCT197 exposure and efficacy/safety endpoints
 6. Change from baseline in mMRC dyspnoea scale over time
 7. BODE index among the three groups at Day 14.

4.4 Safety endpoints

The safety endpoints of this study are:

1. TEAEs/SAEs (from first dose of study drug until study completion)
2. TEAEs of special interest (pneumonia)
3. TEAEs of special interest (liver enzymes [ALT, AST, bilirubin total and fractions], rash, acneiform dermatitis, cervical/vaginal inflammation, headache and pruritus)
4. Vital signs (body temperature, RR, pulse rate, blood oxygen [measured using a pulse oximeter], systolic and diastolic blood pressure)
5. QTc intervals and ECG findings (arrhythmias, conduction blocks, changes in ST segment) at Baseline, from Day 1 to Day 7, Days 10 and 14
6. Laboratory data including sputum cultures and blood eosinophil percentages.

5 SAMPLE SIZE AND POWER

The sample size is based on a formal statistical calculation using the following assumptions:

1. Endpoint: Absolute change in FEV1 (mL) from baseline to Day 7
2. Minimum clinically significant difference between regimens: absolute change of 100 mL
3. Standard deviation (SD) of the difference = 230 mL (based on a previous study [CBCT197A2201] with BCT197)
4. Superiority design of two BCT197 doses compared to placebo
5. Two-sided alpha (Type 1) error = 0.05
6. No adjustment for multiplicity
7. Beta error (Type 2) = 0.20 (Power = 80%).

Based on the above assumptions, 85 subjects will need to be analysed per dose regimen, resulting in a total of 255 evaluable subjects.

Assuming a dropout rate of approximately 5%, a total of approximately 270 subjects will be randomised to the study.

6 ANALYSIS POPULATIONS

All primary and secondary efficacy endpoints will be analysed using the intention-to-treat (ITT) population. The Per-Protocol (PP) population will be used for the analysis of the primary endpoint to examine the robustness of the primary analyses. A PP analysis will also be performed on the secondary and exploratory efficacy endpoints for this Proof of Concept (PoC) and hypothesis-generating study.

Safety and tolerability will be analysed using the safety population.

Pharmacokinetic data will be analysed using the PK population.

6.1 Intention-To-Treat population (ITT)

The ITT population includes all subjects who:

- Are randomised, and
- Receive at least one dose of study medication, and
- Provide a Baseline and at least one post-Baseline FEV1 value.

Patients will be included in the analysis per the treatment to which they were randomised.

Note: the 'Baseline' FEV1 value refers to the last non-missing FEV1 value assessed prior to the first dose of study medication.

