9.3.5 Continued study participation

If premature discontinuation of investigational treatment occurs, the subject should continue to attend the follow-up visits until the end of study for collection of data on treatment failure.

The subject should NOT be considered withdrawn from the study due to interrupting or discontinuing investigational treatment. For this study it is very important to continue collecting data, especially outcome data, on all subjects whether or not they complete treatment. The investigator must determine the primary reason for the subject's premature discontinuation of investigational treatment and record this information on the treatment disposition eCRF page. The investigator and study staff must discuss with the subject, the subject's continued participation in the study and request subjects to continue attending follow-up study visits according to the study visit schedule.

If the subject cannot or is unwilling to attend the follow-up visits, all assessments for Week 26 (refer to Schedule of Assessment [Table 9-1](#)) should be performed and the site staff should request to maintain regular phone contact with the subject, or with a person pre-designated by the subject. This phone contact should preferably be done according to the study visit schedule. Data will continue to be collected concerning the subject's health status, including information regarding new / concomitant treatments, adverse events, events of special interest i.e., rash etc., and vital status.

If the subject decides to completely withdraw from the study (refuses any further study participation or contact), all study participation for that subject will cease and data to be collected at subsequent visits will be considered missing.

The appropriate personnel from the site and ICON will assess whether investigational treatment should be discontinued for any subject whose treatment code has been broken inadvertently for any reason.

The investigator must also contact the IRT to register the subject's discontinuation from investigational treatment.

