7.2 Handling of missing data and outliers

7.2.1 Missing data analysis methods

No strategy for imputation of missing values from subjects who dropped out will be applied because the mixed model for repeated measurements analysis done for the primary endpoint is known to produce a valid analysis if the drop-out mechanism is missing at random⁵.

The analysis (and clinical database) will only include those FEV1 results assessed as being of acceptable quality for each time point.

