8.1.8 Exclusion of data from the statistical analysis

Spirometries assessed as being of unacceptable quality will be removed upstream from the clinical database, thus excluded from the statistical analysis.

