8.6.3.12 Number of COPD-related deaths during the study

See section 8.6.3.11 for the derivation of COPD-related deaths.

The proportion of patients with a COPD-related death during the study will be compared between treatment regimens using Fisher’s exact test (two-sided test at 5% alpha level).

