8.6.4 Analysis of exploratory endpoint(s)

The analysis of exploratory endpoints will be performed on the ITT and PP populations.

8.6.4.1 Exploratory composite scale endpoints at Weeks 8, 12 and 26

The cumulative proportion of patients presenting each of the criteria below during the study will be summarised per treatment regimen at Days 30, 60, 90, 120, 150 and 180 and compared between treatment regimens at each timepoint using Pearson’s Chi-square test (or Fisher’s exact test as appropriate) (two-sided test at 5% alpha level):

- Worsening of symptoms warranting the addition of another antibiotic or initiation of a new antibiotic
- Worsening of symptoms warranting an increase in dose of oral corticosteroids or initiation of new oral corticosteroids
- Worsening of symptoms requiring additional treatment regimen of oral corticosteroids and/or antibiotics after completion of the initial regimen
- Re-hospitalisation due to worsening of COPD and requiring additional treatment during the duration of the study due to an exacerbation of respiratory symptoms (emergency room admission for longer than 24 hours will qualify as a hospitalisation)
- COPD-related death.

Moreover, the cumulative incidence of CTF (i.e. any one of the individual criteria above is met) will be evaluated at Days 30, 60, 90, 120, 150 and 180 and compared between treatment regimens at each timepoint using Pearson's Chi-square test (or Fisher's exact test as appropriate) (two-sided test at 5% alpha level).

A bar chart will be presented per treatment regimen showing the cumulative incidence of CTF at Days 30, 60, 90, 120, 150 and 180.

In addition, time to CTF will be analysed using the Kaplan-Meier method. Patients who don't meet any one of the individual criteria above or who are discontinued before having it will be considered as "censored" patients.

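### The set called ITT requires a usable post-baseline FEV1, yet it also governs treatment failure, death and other endpoints that need no spirometry

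*SAP*

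**What the plan says.** SAP 6.1, like protocol 13.3.1, builds the ITT set from patients who were randomised, took at least one dose, and "Provide a Baseline and at least one post-Baseline FEV1 value". No visit is named for the post-baseline value.

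Two further SAP sections mean the value must be usable. Section 8.1.8 states: "Spirometries assessed as being of unacceptable quality will be removed upstream from the clinical database, thus excluded from the statistical analysis". Section 7.2.1 adds that the analysis "will only include those FEV1 results assessed as being of acceptable quality for each time point".

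The set is then used throughout for efficacy. SAP 6 says: "All primary and secondary efficacy endpoints will be analysed using the intention-to-treat (ITT) population". SAP 8.6.4 says: "The analysis of exploratory endpoints will be performed on the ITT and PP populations". The PP set is a subset of ITT (SAP 6.3). The randomised population in SAP 6.5 is defined for tables and listings only.

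For outcome collection, protocol 9.3.5 says that "it is very important to continue collecting data, especially outcome data, on all subjects whether or not they complete treatment".

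**The concern.** Several endpoints analysed on this set do not depend on spirometry: COPD-related death, number of and time to exacerbations, readiness for discharge, EXACT-PRO, respiratory rate and clinical treatment failure. For these, membership rests on something that happens after randomisation and that treatment could influence: being alive, present and able to give an acceptable blow at least once. A dosed patient who never does so leaves both numerator and denominator, even when the outcome is known. If such patients are unevenly spread across arms, the comparison is no longer one of randomised groups. None of the sensitivity analyses in SAP 8.6.2.3 restores them; all concern FEV1 and stay within ITT or PP.

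**Working it through.** **Who is excluded.** Spirometry is scheduled on Days 2 to 7, 10 and 14 and at Weeks 8, 12 and 26 (protocol Table 9-1). One usable value at any of these visits, with a usable baseline, is enough. The excluded patients are dosed patients with no usable value at all of these visits: very early deaths, early complete withdrawals, and patients never able to give an acceptable effort. A missing or unusable baseline FEV1 also excludes a patient. That value is taken before the first dose, so treatment cannot affect it, and it costs data rather than causing treatment-related selection.

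**Which endpoints move.**

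- *Clinical treatment failure.* SAP 7.1.4.13, criterion 5, takes death from the AE form and includes the initial exacerbation. A very early COPD death is therefore a failure that the set removes. This is the main effect.
- *COPD-related death.* SAP 8.6.3.12 says: "The proportion of patients with a COPD-related death during the study will be compared between treatment regimens". It takes its derivation from 8.6.3.11, which uses the 'Acute Exacerbation COPD' form and counts only exacerbations whose symptoms start on or after first dosing. The form question cited under criterion 4 concerns events after the qualifying exacerbation has subsided. A death from the index exacerbation appears to be missed whichever set is used, so the effect of the set alone is smaller.
- *Time to next exacerbation.* The clock starts when current symptoms stop (SAP 7.1.4.10). A very early death hardly contributes.
- *Discharge readiness.* Deaths are censored at death (SAP 7.1.4.11, Table 5). A very early death adds little.
- *EXACT-PRO and respiratory rate.* A very early death supplies few or no post-baseline values. A patient who is followed but never gives an acceptable blow can supply full data on these endpoints, and on exacerbations and discharge, and all of it is lost from the efficacy comparison.

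**Size, on assumed counts.** The plan gives no number of patients without a usable FEV1 and no failure rate, so there is no figure of its own to reproduce on this point. Inputs from SAP 5 are about 270 randomised and 255 evaluable. Per arm that is 270/3 = 90 and 255/3 = 85, a difference of 5. I use 5 only as the top of an illustrative range; it is the general dropout allowance, not an estimate of patients with no FEV1. I assume that all 90 are dosed.

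Let x be the failures among n = 90, and let k excluded patients all be failures. The set then shows (x − k)/(n − k) in place of x/n.

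| Assumed true rate | k = 1 | k = 3 | k = 5 |
|---|---|---|---|
| 18/90 = 20.0% | 17/89 = 19.1% | 15/87 = 17.2% | 13/85 = 15.3% |
| 27/90 = 30.0% | 26/89 = 29.2% | 24/87 = 27.6% | 22/85 = 25.9% |
| 36/90 = 40.0% | 35/89 = 39.3% | 33/87 = 37.9% | 31/85 = 36.5% |

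The understatement in that arm runs from 0.7 points (40.0 − 39.3) to 4.7 points (20.0 − 15.3). It carries over in full to the difference between arms only if the other arm loses no one. Counting every excluded patient as a failure is the extreme case, because early withdrawals may not be failures.

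**The case against.** The case for leaving the plan alone has real substance.

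- A reader might infer that missing the Day 2 spirometry is enough to be dropped. It is not: any later usable value qualifies. Ventilated patients stay in the study to Week 26 (protocol 10.6.1). Patients who stop treatment and cannot attend visits are still asked for the Week 26 assessments (9.3.5), as are those whose participation the investigator ends (9.3.3). Week 26 includes spirometry. Patients needing intensive care or ventilation at entry are excluded from the trial. The affected group is therefore narrow.
- A reader might infer that the follow-up of excluded patients goes unused. It does not. Every dosed patient is in the safety population, AEs leading to death are tabulated by regimen, and events on the exacerbation form enter the AE tables (SAP 8.7.1). Listings cover all randomised patients (8.1.9), and exclusions from ITT are summarised by regimen with reasons (8.3), so an imbalance would be visible.
- Protocol 13.5.1 treats all analyses as exploratory, and SAP 6 calls the study hypothesis-generating. The set is defined the same way in both documents, and protocol 13.3.1 also labels it the Full Analysis Set.

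All of this stands and limits the size of the point. It does not remove it. The safety summaries carry no test (SAP 8.7), group patients by treatment received (6.2), and give no treatment-failure or discharge comparison. The efficacy comparisons are tested at 5% on a set selected partly by outcome.

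**Conclusion.** The point holds in a limited form. One set conditional on FEV1 governs all efficacy endpoints, and no planned efficacy analysis restores the dosed patients whom it drops. Clinical treatment failure is the endpoint most affected; COPD-related death, exacerbations and discharge readiness are affected less. The primary FEV1 analysis is not touched.

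The number of patients is unknown and probably small. The range of 0.7 to 4.7 percentage points rests on assumed failure rates, on 1 to 5 exclusions in an arm of 90, and on every excluded patient being a failure.

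A reader might go further and conclude that the set rule could by itself decide the Fisher test of COPD-related death, by removing patients who die of the index exacerbation. The documents do not support that. Under SAP 8.6.3.11 those deaths appear to fall outside the count in any population, so the source of the death endpoint is a separate gap that changing the set would not close.

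**What to change.** 1. Keep the FEV1 condition for spirometry endpoints only.
2. Analyse clinical treatment failure, COPD-related death, exacerbations, time to next exacerbation, discharge readiness, EXACT-PRO and respiratory rate in all randomised patients who received at least one dose, by randomised arm. State the same set for the adjudicated analyses in SAP 8.8.1, which names none.
3. Reconcile the source of COPD-related death between SAP 8.6.3.11 and 8.6.3.12 (exacerbation form) and SAP 7.1.4.13, criterion 5 (AE form), so that deaths from the index exacerbation are counted.
4. Record these changes in SAP section 9, since protocol 13.3 and 13.4.2 assign the secondary endpoints to ITT.

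The cost is SAP wording, one population flag and a revised derivation for the death endpoint. Data collection and sample size do not change.

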6.2 Safety population (Safety)

The safety population includes all subjects who received at least one administration of the study medication.

Patients will be included in the analysis per the treatment actually/1st received.

6.3 Per-Protocol population (PP)

The PP population is a subset of the ITT population and includes all randomised subjects who have been treated according to the protocol and fulfil the following criteria (i.e. no major protocol deviations):

- Key inclusion/exclusion criteria met with respect to factors likely to affect the assessment of efficacy in the intended target population
- Absence of relevant protocol violations with respect to factors likely to affect the efficacy of treatment where the nature of protocol violation will be defined before breaking the blind
- Adequate study medication compliance (i.e. full treatment regimen; all 3 doses of study drug received on Days 1, 3, and 5)
- Adequate measurement of the primary variable (i.e. Baseline and Day 7 FEV1 values provided).

Patients will be included in the analysis per the treatment to which they were randomised.

6.4 PK population

For the nonlinear mixed effects modelling, all subjects who received at least one dose administration and have at least one quantifiable plasma concentration will be included.

6.5 Other Populations Defined for Tables and Listings

For the purposes of tables and listings a further three populations are defined:

- All screened patients
- Screening failure patients
- Randomised population (all randomised patients).

6.6 Protocol deviations/violations and exclusions from analysis sets

All violations and exclusions of patients from analysis populations will be finalised at the Classification Meeting prior to the final database lock (DBL)/study unblinding, through clinical review input provided by Mereo, using the following sources of information:

- Supportive patient listings, provided by the ICON lead statistician ahead of the Classification Meeting, based on data recorded on the eCRF.
The protocol deviations criteria are detailed in Appendix B and specific protocol deviations will be identified by programming.
- Protocol Deviation Logs, retrieved from Clinical Trial Management System (CTMS).

Further, deviations from protocol will be classified as major or minor.

7 STATISTICAL CONSIDERATIONS AND ANALYSIS

7.1 Derived Variables

7.1.1 Study days

Study days will be based on the date of first IMP administration (Study Day 1) and calculated as:

- (assessment date – date of first IMP administration) + 1, for assessments on or after the first IMP administration date
- (assessment date – date of first IMP administration), for assessments prior to first IMP administration date.

7.1.2 Follow-up time

Follow-up time (days) will be calculated as:

(date of last contact - date of first IMP administration) + 1

7.1.3 Definitions relative to demographic and other baseline characteristics

7.1.3.1 Age

Age at informed consent will be calculated as:

Age (years) = (date of informed consent - date of birth + 1) / 365.25

7.1.3.2 Weight, height and BMI

Weight, recorded in pounds on the eCRF, will be converted in kilograms (1 pound = 0.45359 kg).

Height, recorded in inches on the eCRF, will be converted in centimetres (1 inch = 2.54 cm) (International System of Units).

Body mass index (BMI) will be calculated in kg/m² as: weight (kg)/(height (m))².

7.1.3.3 Temperature

Temperature, recorded in Fahrenheit degrees on the eCRF, will be converted in Celsius degrees:

Celsius degrees = (Fahrenheit degrees - 32) x (5/9)

7.1.3.4 Smoking duration

Duration of smoking will be calculated in years as:

- Current smoker: (Current Year - Year when subject started smoking) + 1
- Ex-smoker: (Year when subject stopped smoking - Year when subject started smoking) + 1

7.1.3.5 COPD disease duration

Duration of COPD disease will be calculated in years as:

(date of informed consent – date of first diagnosis of COPD + 1) / 365.25

7.1.3.6 Current COPD exacerbation duration

- Duration of current COPD exacerbation symptoms will be calculated in days as:
(date when symptoms stopped – date when symptoms started + 1)
- Time until complete recovery from the current COPD exacerbation will be calculated in days as:
(date when patient achieved complete recovery from the current exacerbation – date when symptoms started).

Where ‘Date when symptoms started’, ‘Date when symptoms stopped’, and ‘Date when patient achieved complete recovery from the current exacerbation’ are recorded on the ‘Current COPD Exacerbation’ form of the eCRF.

7.1.3.7 Times from start/stop of current COPD exacerbation to first dosing

Times from start/stop of current COPD exacerbation symptoms to first dose of study medication will be calculated in days as:
(date of first study treatment dose – date when symptoms started/stopped).

7.1.3.8 Time since last documented COPD exacerbation

Time since last documented COPD exacerbation will be calculated in months as:
(date of informed consent – date of last documented COPD exacerbation + 1) / 30.4375

7.1.4 Definitions relative to efficacy criteria

7.1.4.1 COPD exacerbation (moderate and severe)

A COPD exacerbation is defined as “*A sustained worsening of the patient’s condition (dyspnoea, cough and/or sputum production/purulence), from the stable state and beyond normal day-to-day variations, that is acute in onset and necessitates a change in regular medication in a patient with underlying COPD that includes prescriptions of systemic corticosteroids and/or antibiotics or need for hospitalisation*”.

The exacerbations will be classified as moderate or severe as per the EMA/CHMP guideline definition:

- Moderate: exacerbations that require treatment with systemic corticosteroids and/or antibiotics
- Severe: exacerbations that require hospitalisation or result in death.

7.1.4.2 FEV1 normalisation

FEV1 normalisation is achieved if FEV1 returns to a value $\geq 89\%^3$ of the most recent FEV1 value measured within the last 12 months outside an exacerbation (pre-study FEV1 value).

7.1.4.3 FEV1/FVC normalisation

FEV1/FVC normalisation is achieved if FEV1/FVC returns to a value $\geq 89\%$ ³ of the most recent FEV1/FVC value measured within the last 12 months outside an exacerbation (pre-study FEV1/FVC value).

7.1.4.4 Time to improvement in FEV1 value

7.1.4.4.1 Time to improvement of 100 mL in FEV1

This is defined as the time (in days) from initiation of study treatment until the change in FEV1 is $\geq +100$ mL (improvement).

Change in FEV1 = FEV1 value (time T) – FEV1 value (baseline).

Table 2-1: Criteria for event/censored for assessment of Time to improvement of 100 mL (FEV1)

Situation	Date of event or Censoring	Time to improvement of 100 mL	Outcome
Subjects who meet criteria of change in FEV1 $\geq +100$ mL	Date when the criteria is met	Time from initiation of study treatment until Date when the aforesaid criteria is met	Event
Subjects who never meet change in FEV1 $\geq +100$ mL	Date of the last evaluable spirometry	Time from initiation of study treatment until Date of the last evaluable spirometry	Censored
Subjects who died	Death date	Time from initiation of study treatment until Date of death	Censored
Subjects who withdrew or were lost to follow-up during the study	Withdrawal or last contact date	Time from initiation of study treatment until Date of withdrawal or last contact date	Censored

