Subjects who were not medically ready for discharge from hospital	Withdrawal or last contact date	Time from hospitalisation admission until Date of withdrawal or last contact date	Censored
Subjects who died	Death date	Time from hospitalisation admission until Date of death	Censored
Subjects who withdrew or were lost to follow-up during the study	Withdrawal or last contact date	Time from hospitalisation admission until Date of withdrawal or last contact date	Censored

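### SAP Tables 2-1, 2-2 and 3 give a non-improver who withdraws, is lost or dies two possible censoring dates, and censoring deaths there and in Table 5 makes the reported probabilities slightly too high.

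*SAP*

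**What the plan says.** SAP 7.1.4.4.1, Table 2-1, has three rows for subjects without a 100 mL gain. Those who never reach it are censored at the "Date of the last evaluable spirometry". Those who died are censored at the death date. Those who withdrew or were lost are censored at the "Withdrawal or last contact date". Table 2-2 (80 mL) is identical in structure. Table 3 (EXACT-PRO improvement and recovery) follows the same pattern, with the last evaluable EXACT-PRO assessment in place of spirometry.

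Table 5 (SAP 7.1.4.11, discharge readiness) uses the withdrawal or last contact date for both the not-ready row and the withdrawal row. Its death row is "Time from hospitalisation admission until Date of death", also censored.

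SAP 8.6.3.3, 8.6.3.7, 8.6.3.8 and 8.6.3.14 plan Kaplan-Meier curves, period-by-period probabilities of the event with 95% CIs, and pairwise log-rank tests. For the FEV1 and EXACT-PRO endpoints these sections say that subjects without the event, or discontinued before it, are censored; for discharge readiness, 8.6.3.14 says so of discontinued subjects. None names a date. No competing-risk estimate is planned.

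**The concern.** There are two separate faults.

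**Two dates.** In Tables 2-1, 2-2 and 3 a non-improver who withdraws or is lost satisfies both the never-improved row and the withdrawal row. A non-improver who dies satisfies both the never-improved row and the death row. Without precedence, two programmers can follow the SAP and draw different curves. The rows are not equally good. An FEV1 gain can be seen only at spirometry and an EXACT-PRO improvement only from diary entries, so a subject censored at a later contact date sits in the risk set while no event can be recorded. That pulls the estimated probability down. Protocol 9.3.8 shows how the gap can arise: a subject lost to follow-up is traced through third parties and public sources, and a last-known-alive date is recorded.

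**Deaths.** A subject who dies before improving, or before being ready for discharge, can never have the event. Kaplan-Meier censoring treats that subject as someone who would have gone on like the survivors, so 1 minus Kaplan-Meier is too high as a statement of the proportion who improve or become ready. The SAP labels it as exactly that probability. This applies to all four tables.

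**Working it through.** **The plan's own figure.** The documents give no expected event or death rate for these endpoints. The only stated figure is the primary sample size: 100 mL, SD 230 mL, two-sided 5%, 80% power. 2 × (1.960 + 0.842)² × (230/100)² = 83.04, so 84 by the normal formula. The t-test gives power 79.99% at 84 and 80.5% at 85, so the stated 85 per arm reproduces. 255/0.95 = 268.4, against about 270 stated. This does not test the present point, but it supplies a scale: 255 completers from 270 means 15 exits of any kind, 15/270 = 5.6%, about 5 per arm of 90.

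**Assumptions (not in the documents).** Exponential time to improvement with median 7 days, seen at the protocol's spirometry days. A fraction f of the arm exits, uniformly over Days 1 to 14.

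**Deaths censored or competing.** With censoring, 1 minus Kaplan-Meier at Day 14 is 1 − 2^(−14/7) = 75.0%. With death as a competing event, the probability falls by f × Σ p(v) × G(v). Here p(v) is the probability that improvement is first seen at visit v, and G(v) = (v − 1)/13 is the share of exits that occur before v.

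| Visit day | p(v) | G(v) | product |
|---|---|---|---|
| 2 | 0.1797 | 0.0769 | 0.0138 |
| 3 | 0.0773 | 0.1538 | 0.0119 |
| 4 | 0.0700 | 0.2308 | 0.0162 |
| 5 | 0.0634 | 0.3077 | 0.0195 |
| 6 | 0.0575 | 0.3846 | 0.0221 |
| 7 | 0.0520 | 0.4615 | 0.0240 |
| 10 | 0.1285 | 0.6923 | 0.0890 |
| 14 | 0.1215 | 1.0000 | 0.1215 |

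The sum is 0.318. At f = 2% the excess is 0.6 points. At f = 5.6%, treating all the planned attrition as early deaths, it is 1.8 points (75.0% against 73.2%). At Day 7 the sum is 0.1075, so 0.6 points at f = 5.6%. By Day 56 the sum is 0.564, so 3.2 points (99.6% against 96.4%). At f = 20% the Day 14 excess is about 6.3 points.

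A continuous-time version for discharge readiness assumes a median of 8 days and deaths uniform over Days 0 to 14. 1 minus Kaplan-Meier at Day 14 is 1 − 2^(−14/8) = 70.3%, and the excess is 0.282 × f. That gives 0.3, 0.8 and 1.4 points at f = 1%, 3% and 5%.

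**Two dates for withdrawals.** Same 7-day model, f = 5.6%, simulated. Censoring at last spirometry gives 75.0% at Day 14. Censoring at a contact 28 days after exit gives 73.2%, because every early exit is still counted at risk on Day 14. At Day 56 both give 99.6%.

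**The log-rank test.** 3,000 simulated trials per scenario, 90 per arm, no effect on the improvement hazard; Monte Carlo standard error about 0.4 points at 5%.

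| Exits, arm 1 v arm 2 | Censored at exit or at last spirometry | Kept at risk to Week 26 |
|---|---|---|
| 5.6% v 5.6% | 4.9% | 5.3% |
| 0% v 11.1% | 4.2% | 14.8% |
| 2% v 20% | 5.1% | 27.9% |

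The last column is the extreme: last contact at Week 26, or death counted as never improving to the end of follow-up.

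**The case against.** The strongest defence is that censoring at death is a legitimate choice of estimand. Together with log-rank it compares cause-specific hazards, and the simulation shows that the test keeps its level even with unequal exits. That stands. What it does not defend is reading 1 minus Kaplan-Meier as the probability of improvement or readiness.

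A reader might infer from protocol 9.3.5, where sites are asked to "maintain regular phone contact with the subject", that last contact will routinely fall months after the last spirometry. The documents do not support this. That section concerns subjects who stopped treatment or visits, says that stopping treatment does not make them withdrawn, and asks for the Week 26 assessments. Those subjects belong in the last-spirometry row. Subjects who fully withdraw refuse further contact, so their withdrawal date should lie close to the last assessment. The long gap is confined to subjects lost to follow-up, for whom 9.3.8 is the relevant text. For Table 3 the withdrawal row is further limited to the observed period, Days 1 to 29.

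A reader might also infer that the two-date conflict reaches discharge readiness. It does not, because Table 5 uses one date for both rows.

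Nor do the documents support saying that harm would be masked. COPD-related death is a secondary endpoint with its own Fisher test (SAP 8.6.3.12), adverse events leading to death are tabulated by regimen (SAP 8.7.1), and withdrawals are tabulated with reasons (SAP 8.2).

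Finally, these are secondary endpoints in a study whose protocol calls all analyses exploratory, and the primary repeated-measures analysis is untouched. That limits the importance of the point but does not remove it.

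**Conclusion.** The point holds at low severity. The overlap in Tables 2-1, 2-2 and 3 follows from the text alone and needs no assumption. The overstatement from censoring deaths applies to all four tables. Its size, about 0.3 to 1.8 points at Day 14, rests on assumed early death fractions of 1% to 5.6%, assumed medians of 7 to 8 days and exponential times. The upper end puts the plan's whole attrition into early deaths. It is also slightly high for the FEV1 tables, because the ITT set requires a post-baseline FEV1 and about one in thirteen of the assumed exits falls before Day 2.

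The two faults push the curve in opposite directions: death censoring raises it and a late contact date lowers it. It would therefore be wrong to describe a single bias with a known sign. The log-rank comparison is affected materially only if exits differ between arms and those subjects are held at risk long after their last assessment. The documents give no figure from which to predict such an imbalance.

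**What to change.** - **Tables 2-1, 2-2 and 3:** censor withdrawn and lost subjects without the event at the last evaluable spirometry or EXACT-PRO assessment, and state which row takes precedence when a subject fits more than one.
- **Tables 2-1, 2-2, 3 and 5:** report the period probabilities as cumulative incidence, with death before the event as a competing event. Keep the log-rank test and label it as the comparison of cause-specific hazards.
- **Optional sensitivity analysis:** treat deaths as never improved, or never ready, to the end of the observation window. It should not replace the main comparison, because it answers a different question and, as the simulation shows, rejects when only the exit rates differ.

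The cost is a short SAP edit before unblinding, slightly more programming and slightly lower stated probabilities. No new data are needed.
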